1. VERSION HISTORY

Table 1. Summary of Changes

Version/ Date	Associated Protocol Amendment	Rationale	Specific Changes
1 10 AUG2022	Original 18 May 2022	N/A	N/A

2. INTRODUCTION

PF-07081532 is an oral GLP-1R agonist that is currently being investigated as a chronic therapy to improve glycemic control in adult participants with T2DM. Based on review of the effect of hepatic impairment on human PK for compounds cleared in a similar manner to PF-07081532 (OATP-mediated hepatic uptake), impaired hepatic function is generally associated with increased drug exposures in plasma.

Therefore, the primary purpose of this study is to characterize the effect of varying degrees of hepatic impairment on the plasma PK of PF-07081532 following administration of a single oral dose of PF-07081532.

This statistical analysis plan (SAP) provides the detailed methodology for summary and statistical analyses of the data collected in Study C3991009.

2.1. Modifications to the Analysis Plan Described in the Protocol

Not Applicable

2.2. Study Objectives, Endpoints, and Estimands

Objectives	Endpoints
Primary:	Primary:

 To compare the PK of PF-07081532 following administration of a single oral dose in adult participants with varying degrees of hepatic impairment relative to age- and body weight-matched participants without hepatic impairment. 	
 Plasma: C_{max}, AUC_{inf}, AUC_{last}^*, f_u, $C_{max,u}$, $AUC_{inf,u}$ and $AUC_{last,u}^*$, as data permit.
Secondary:	Secondary:

 To evaluate the safety and tolerability of a single oral dose of PF-07081532 when administered to adult participants with varying degrees of hepatic impairment and in age- and body weight-matched participants without hepatic impairment. 	
 Assessment of treatment emergent AEs, clinical laboratory abnormalities, vital signs, ECG parameters.
CCI [REDACTED]	[REDACTED]
[REDACTED]	[REDACTED]

Objectives	Endpoints
CCI	
■ [REDACTED]	■ [REDACTED]

* AUC_{last} and $AUC_{last,u}$ will be treated as primary endpoints if data do not permit robust estimation of AUC_{inf} and $AUC_{inf,u}$.
 CCI [REDACTED]

2.2.1. Primary Estimand(s)

Not applicable because C3991009 is a Phase 1 study with no estimands on PK endpoints

2.2.2. Secondary Estimand(s)

Not applicable because C3991009 is a Phase 1 study with no estimands on safety endpoints

2.2.3. Additional Estimand(s)

Not applicable because C3991009 is a Phase 1 study with no estimands on safety endpoints

2.3. Study Design

This is an open-label, single-dose, parallel-group, multicenter study to investigate the effect of varying degrees of hepatic function on the plasma PK of PF-07081532 after a single, oral 20 mg dose administered in the fed state (standard breakfast). Safety and tolerability will be evaluated throughout the study. A total of approximately 24 participants with varying degrees of hepatic function will be dosed in the study as shown in Table 2. If recruitment of participants with severe hepatic impairment proves prohibitive, the number of participants to be enrolled in this group may be flexible (4-6 participants).

Table 2. Hepatic Function Categories Based on Child-Pugh Score

Group	Description	Child-Pugh Score	Number of Participants
1	Without hepatic impairment	Not Applicable	6 ^a
2	Mild hepatic impairment	Class A (5 to 6 points)	6
3	Moderate hepatic impairment	Class B (7 to 9 points)	6
4	Severe hepatic impairment	Class C (10 to 15 points)	6 ^b

a. Additional participants may be dosed to a maximum of 8 participants to ensure mean age ± 5 years and mean body weight ± 10 kg of this group is aligned with the pooled average assessed when approximately $\geq 75\%$ of participants are dosed across the other 3 groups.

b. If recruitment proves to be prohibitive, study may dose 4-6 participants in this group.

Categorization of participants into Groups 2-4 will be done based on Child-Pugh scores determined at the screening visit, as described in Appendix 11 of the protocol.

Staged Enrollment of Study Groups

Participants will be dosed in a staged manner as follows:

- *Participants with moderate and severe hepatic impairment (Groups 3 and 4) will be enrolled first.*
- *Recruitment of participants with mild hepatic impairment (Group 2) will initiate when approximately 50% of the participants across Groups 3 and 4 have been dosed.*

Sponsor approval is required before proceeding with recruitment of Group 2.

- *An average value for age and weight for the 3 hepatic impairment groups (Groups 2-4) will be determined, and participants without hepatic impairment (Group 1) will be recruited to match the average demographics (at a minimum, age and weight, and as much as practically possible gender) across the pooled Groups 2-4.*
- *Recruitment for healthy participants in Group 1 (without hepatic impairment) may start when approximately 75% of total participants across Groups 2-4 (ie, approximately 12-13 participants) have been dosed.*

Sponsor approval is required before proceeding with recruitment of Group 1.

3. ENDPOINTS AND BASELINE VARIABLES: DEFINITIONS AND CONVENTIONS

Baseline is defined as the last pre-dose assessment for all endpoints, unless otherwise specified.

3.1. Primary Endpoint(s)

- PF-07081532 Plasma Pharmacokinetic parameters: C_{max} , AUC_{inf} , AUC_{last} , fu , $C_{max,u}$, $AUC_{inf,u}$, $AUC_{last,u}$ as data permit.

The plasma PK parameters in Table 3 will be derived from concentration-time profiles using standard non-compartmental analysis methods (with the exception of fu that will be directly determined by the analytical lab):

Table 3. Summary of Plasma PK Parameters of PF-07081532 to be calculated

Parameter	Analysis Scale	PF-07081532 20mg
C_{max}	ln	A, D
AUC_{inf}^*	ln	A, D
AUC_{last}^+	ln	A, D
fu	R	A, D
$C_{max,u}$	ln	A, D

Pfizer Confidential

$AUC_{inf,u}^*$	ln	A, D
$AUC_{last,u}^+$	ln	A, D

*=if data permits. ⁺ AUC_{last} and $AUC_{last,u}$ will be treated as primary endpoints if data do not permit robust estimation of AUC_{inf} and $AUC_{inf,u}$,

Abbreviations: A = analyzed using a statistical model; D=displayed with descriptive statistics as outlined in Table 7 in Section 6.1.1.1 ; ln=natural-log transformed; R=raw (untransformed).

The plasma PK parameters for unbound PF-07081532 will be calculated as described in Table 4:

Table 4. Summary of Plasma PK parameters of Unbound PF-07081532 to be calculated

Parameter	Method of Determination
$AUC_{last,u}^+$	$fu \times AUC_{last}$
$AUC_{inf,u}^*$	$fu \times AUC_{inf}^*$
$C_{max,u}$	$fu \times C_{max}$

*=if data permits. ⁺ AUC_{last} and $AUC_{last,u}$ will be treated as primary endpoints if data do not permit robust estimation of AUC_{inf} and $AUC_{inf,u}$,

3.2. Secondary Endpoint(s)

Assessment of treatment emergent AEs, clinical laboratory abnormalities, vital signs, ECG parameters.

An adverse event is considered treatment emergent (TEAE) relative to a given treatment if:

- the event starts during the effective duration of treatment (i.e. starting on or after the dose of PF-07081532 but before this dose plus lag time)

The effective duration of treatment is determined by the lag time. Any event occurring within the lag time is attributed to the corresponding treatment. The lag time is defined by the Pfizer Standard of 365 days post last dose of IP.

[figure not shown]
[figure not shown]
[figure not shown]
A 3-tier approach for summarizing AEs will not be used due to the low number of participants planned to be recruited.

The following data are considered in standard safety summaries (see protocol for collection days and list of parameters):

- adverse events,
- laboratory data,
- vital signs data,
- ECG results.

For laboratory, vital signs and ECG data, baseline will be defined as the last pre-dose measurement, unless otherwise specified.

CCI

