#### **8.4.1. Time Period and Frequency for Collecting AE and SAE Information**

The time period for actively eliciting and collecting AEs and SAEs (“active collection period”) for each participant begins from the time the participant provides informed consent, which is obtained before undergoing any study-related procedure and/or receiving study intervention), through and including a minimum of 28 calendar days, except as indicated below, after the last administration of the study intervention.

Follow-up by the investigator continues throughout the active collection period and until the AE or SAE or its sequelae resolve or stabilize at a level acceptable to the investigator.

When a clinically important AE remains ongoing at the end of the active collection period, follow-up by the investigator continues until the AE or SAE or its sequelae resolve or stabilize at a level acceptable to the investigator and Pfizer concurs with that assessment.

For participants who are screen failures, the active collection period ends when screen failure status is determined.

If the participant withdraws from the study and also withdraws consent for the collection of future information, the active collection period ends when consent is withdrawn.

If a participant permanently discontinues or temporarily discontinues study because of an AE or SAE, the AE or SAE must be recorded on the CRF and the SAE reported using the CT SAE Report Form.

Investigators are not obligated to actively seek information on AEs or SAEs after the participant has concluded study participation. However, if the investigator learns of any SAE, including a death, at any time after a participant has completed the study, and they consider the event to be reasonably related to the study intervention, the investigator must promptly report the SAE to Pfizer using the CT SAE Report Form.

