## **10.3. Appendix 3: Adverse Events: Definitions and Procedures for Recording, Evaluating, Follow-Up, and Reporting**

### **10.3.1. Definition of AE**

AE Definition

• An AE is any untoward medical occurrence in a patient or clinical study participant, temporally associated with the use of study intervention, whether or not considered related to the study intervention.

• Note: An AE can therefore be any unfavorable and unintended sign (including an abnormal laboratory finding), symptom, or disease (new or exacerbated) temporally associated with the use of study intervention.

Events Meeting the AE Definition

• Any abnormal laboratory test results (hematology, clinical chemistry, or urinalysis) or other safety assessments (eg, ECG, radiological scans, vital sign measurements), including those that worsen from baseline, considered clinically significant in the medical and scientific judgment of the investigator. Any abnormal laboratory test results that meet any of the conditions below must be recorded as an AE:

• Is associated with accompanying symptoms;

• Requires additional diagnostic testing or medical/surgical intervention;

• Leads to a change in study dosing (outside of any protocol-specified dose adjustments) or discontinuation from the study, significant additional concomitant drug treatment, or other therapy.

• Exacerbation of a chronic or intermittent preexisting condition, including an increase in either frequency and/or intensity of the condition.

• New condition detected or diagnosed after study intervention administration, even though it may have been present before the start of the study.

• Signs, symptoms, or the clinical sequelae of a suspected drug-drug interaction.

• Signs, symptoms, or the clinical sequelae of a suspected overdose of either study intervention or a concomitant medication. Overdose per se will not be reported as an AE or SAE unless it is an intentional overdose taken with possible suicidal/self-harming intent. Such overdoses should be reported regardless of sequelae.

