#### Assessment of Intensity

The investigator will make an assessment of intensity for each AE and SAE reported during the study and assign it to 1 of the following categories:

- Mild: A type of AE that is usually transient and may require only minimal treatment or therapeutic intervention. The event does not generally interfere with usual ADL.
- Moderate: A type of AE that is usually alleviated with additional specific therapeutic intervention. The event interferes with usual ADL, causing discomfort, but poses no significant or permanent risk of harm to the research participant.
- Severe: A type of AE that interrupts usual ADL, or significantly affects clinical status, or may require intensive therapeutic intervention.

An event is defined as "serious" when it meets at least 1 of the predefined outcomes as described in the definition of an SAE, NOT when it is rated as severe.

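### The TEAE definition in SAP 3.2 rests on start date alone, so an AE recorded before dosing, ongoing at the dose and worse afterwards is not counted unless it is re-entered

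*SAP*

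**What the plan says.** SAP Section 3.2 lists the secondary endpoint as "Assessment of treatment emergent AEs, clinical laboratory abnormalities, vital signs, ECG parameters". It then gives a single condition for a TEAE: "the event starts during the effective duration of treatment", which it explains as "starting on or after the dose of PF-07081532 but before this dose plus lag time". The window is long at its far end: "The lag time is defined by the Pfizer Standard of 365 days post last dose of IP". A further sentence says "Any event occurring within the lag time is attributed to the corresponding treatment". No second limb covers an event that is present before the dose and becomes worse afterwards. The protocol expands the TEAE abbreviation but does not define the term.

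On collection, protocol Section 8.4.1 says that the active period "begins from the time the participant provides informed consent". Section 8.1 allows screening up to 28 days before dosing, so AEs with a pre-dose onset will be on the CRF.

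On what counts as an AE, protocol Section 10.3.1 includes "Exacerbation of a chronic or intermittent preexisting condition, including an increase in either frequency and/or intensity of the condition". Its list of events that are not AEs leaves out day-to-day fluctuation only where the condition does not worsen.

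On recording, protocol Section 10.3.3 says "The investigator will make an assessment of intensity for each AE and SAE reported during the study". It does not say what the site should do when the intensity of an AE already on the CRF rises. The follow-up text in the same section sends new or updated information to the documents first submitted.

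**The concern.** A definition based only on start date works when every event of interest begins after the dose. Here AE collection opens up to four weeks earlier, so some AEs may be open at the time of dosing. If the drug aggravates one of them, the clinically relevant change happens after the dose while the record carries an onset date before it. A programmer following SAP 3.2 as written would leave that record out of the TEAE tables.

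TEAEs are the first-listed component of the secondary endpoint, and the groups are small. Symptomatic AEs also lack the second route that measured variables have through the vital-sign, ECG and laboratory summaries. In a multicenter study, whether a worsening is counted could then depend on each site's habit in opening new records.

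**Working it through.** The plan has no figure on this point to reproduce, and safety is descriptive only (SAP 6.2). The check is therefore to run each kind of event through the rules as written.

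1. **AE that begins after the dose.** It meets the start-date condition and is a TEAE.
2. **Medical-history condition that is exacerbated after the dose.** Protocol 10.3.1 makes the exacerbation the AE. Its onset is the date of the exacerbation, so it meets the start-date condition and is a TEAE.
3. **Measured worsening in vital signs or ECG.** SAP 6.2.3 and 6.2.4 summarise change from the last pre-dose value, so the shift is visible whatever the AE coding. Laboratory data are summarised separately under SAP 6.2.2.
4. **AE that begins between consent and dosing, is ongoing at the dose, and then increases in severity.** The record has a pre-dose start date, and nothing legible tells the site to open a new one. The follow-up text in protocol 10.3.3 leans towards updating the existing record, although it does not mention onset date or intensity. If the record is kept, the event fails the start-date condition and is not a TEAE. SAP Section 6 confines pre-baseline data to listings unless stated otherwise.

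Only case 4 is lost. The attribution sentence in SAP 3.2 speaks of events occurring, rather than starting, within the lag time. But it says which treatment an event belongs to and does not add to the condition for being a TEAE.

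**Scale of one lost event.** Group sizes come from SAP Table 2 (6 per group; Group 4 may have 4 to 6, Group 1 up to 8) and the planned total of about 24. If one participant has a case 4 event and no other TEAE, incidence falls by 1/n:

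- n = 6: 1/6 = 16.7 percentage points
- n = 4: 1/4 = 25.0 points
- n = 8: 1/8 = 12.5 points
- all participants: 1/24 = 4.2 points

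If the participant has another TEAE, participant-level incidence does not change and only the event count and the worst intensity can. The documents give no rate of screening-period AEs and no rate of their worsening, so an expected loss cannot be computed.

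**The case against.** The strongest reply is that protocol 10.3.1 already covers the main scenario. Symptoms of chronic liver disease in Groups 2-4 are usually present at consent, so they are pre-existing conditions and their post-dose exacerbation is a new AE. This stands, and it confines the point to case 4. It does not remove case 4, because 10.3.1 does not say that an AE already on the CRF receives a second record when it worsens.

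Case 4 should also be uncommon. Groups 2-4 need stable disease for 28 days before screening (protocol 5.1.3), eligibility is checked again on Day -1 and Day 1 (Table 1), and rescreening of these groups after mild intercurrent illness waits for resolution (5.4). This stands too.

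A third reply is that the missing rule may sit elsewhere. Protocol 10.1.7 refers to a separate document of CRF completion requirements, and SAP 6.2.1 defers AE summaries to sponsor reporting standards. Neither is available here, so the rule cannot be shown to be absent from them. Even so, the SAP states its own definition, and that definition is incomplete unless such a rule exists.

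Finally, the information is not destroyed. AEs are recorded from consent, SAEs are reported whatever their TEAE status, and listings for about 24 participants can be read one by one. This limits the harm but does not correct the summary tables.

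**Conclusion.** SAP 3.2 would misclassify one specific kind of event: an AE that starts between consent and dosing, is ongoing at the dose and then increases in severity, unless the site re-enters it. The number of such events is unknown and probably small. Each affected participant with no other TEAE moves group incidence by 16.7 points at n=6, or 25 at n=4. The conclusion assumes that the unseen CRF guidance and sponsor standards do not already supply a rule.

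A reader might infer three stronger things, none of which the documents support.

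- *All worsening of pre-dose problems is dropped.* Cases 2 and 3 above show otherwise.
- *The comparison is biased towards better tolerability in hepatic impairment.* The direction is plausible: Group 1 must be free of clinically relevant abnormalities, while Groups 2-4 have chronic disease and background medication. But no document gives AE rates by group before dosing, and expected signs of the underlying disease are not AEs unless more severe than expected.
- *Nausea and vomiting are the events most at risk.* They were the most frequent TEAEs in the earlier single-dose study (protocol 2.2.4.1). However, a post-dose vomiting episode would ordinarily be a new event. Protocol 4.3 also reports that a single 30 mg dose had an AE profile no different from placebo, with vomiting seen at 100 and 200 mg, whereas this study gives 20 mg.

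**What to change.** Choose one of two mechanisms.

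- **In the definition.** Add a second limb to SAP 3.2: *or the event started before dosing and increased in severity on or after dosing*. State that each worsening is counted once. This needs the date of the intensity change to be captured, which the documents do not show.
- **In the recording.** State that post-dose worsening of an AE already on the CRF is entered as a new AE with its own onset date and intensity. The existing start-date rule then works unchanged.

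Do not adopt both. Flagging the old record and also opening a new one could count the same worsening twice. If the CRF guidance already contains the second rule, a cross-reference in SAP 3.2 is enough.

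The cost is one sentence in the SAP or one line in the CRF guidance. The only possible extra data item is a dated change in intensity. Design, sample size and the PK analyses are unaffected.

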3.4. Baseline Variables

Not Applicable.

3.5. Safety Endpoints

See Section 3.2

4. ANALYSIS SETS (POPULATIONS FOR ANALYSIS)

Data for all participants will be assessed to determine if participants meet the criteria for inclusion in each analysis population prior to unblinding and releasing the database and classifications will be documented per standard operating procedures.

For purposes of analysis, the following analysis sets are defined:

Participant Analysis Set	Description
Enrolled	“Enrolled” means a participant’s, or their legally authorized representative’s, agreement to participate in a clinical study following completion of the informed consent process and assignment to study intervention. A participant will be considered enrolled if the informed consent is not withdrawn prior to participating in any study activity after screening. Potential participants who are screened for the purpose of determining eligibility for the study, but do not participate in the study, are not considered enrolled, unless otherwise specified by the protocol.
Safety analysis set	All participants assigned to study intervention and who take at least 1 dose of study intervention.
PK Concentration Set	The PK concentration population is defined as all participants who received at least 1 dose of PF-07081532 and in whom at least 1 plasma concentration value is reported.
PK Parameter Set	The PK parameter analysis population is defined as all participants who received at least 1 dose of PF-07081532 and have at least 1 of the PK parameters of interest calculated.
CCI	

5. GENERAL METHODOLOGY AND CONVENTIONS

The following group labels (or similar) will be used for tables and figures unless otherwise stated:

Group	Description of Group	Label
1	Normal hepatic function	Without Hepatic Impairment
2	Mild hepatic impairment	Mild Hepatic Impairment
3	Moderate hepatic impairment	Moderate Hepatic Impairment
4	Severe hepatic impairment	Severe Hepatic Impairment

5.1. Hypotheses and Decision Rules

There is no statistical hypothesis testing planned for this study and no statistical decision rules will be applied.

5.2. General Methods

5.2.1. Analyses for Continuous Endpoints

Unless otherwise stated, continuous endpoints and relevant safety endpoints will be presented using summary statistics: number of observations, arithmetic mean, standard deviation, median, minimum and maximum values.

5.2.2. Analyses for Categorical Endpoints

Categorical endpoints and relevant safety endpoints will be presented using summary statistics: number of observations, counts and percentages.

[figure not shown]
5.2.3. One-way Analysis of Variance (ANOVA)

The *one-way analysis of variance (ANOVA)* model will include group as a factor.

Estimates of the adjusted mean differences (Test - Reference), and corresponding 90% CIs, will be obtained from the model. These will be exponentiated to provide estimates of the ratio of adjusted geometric means (Test/Reference) and 90% CIs for the ratios. Example SAS code is given in Appendix 1.

Residuals from the models will be examined for normality and the presence of outliers via visual inspection of plots of residuals vs predicted values and normal probability plots of residuals but these will not be included in the clinical study report. If there are major deviations from normality or outliers (where studentized residuals are greater than 3 or less than - 3) then the effect of these on the conclusions may be investigated through alternative transformations and/or analyses excluding outliers. Justification for any alternative to the planned analysis will be given in the report of the study if applicable.

CCI

